1.2 BACKGROUND AND SIGNIFICANCE

There are 39 million Americans over age 65;¹⁻² and 42% of older adults report problems with function, which can lead to difficulty with activities of daily living (ADLs),³ falls and nursing home placement.⁴ Consequently, implementing evidence-based models focused on aging-in-place in older adults is a public health priority. One evidence-based model is Community Aging in Place, Advancing Better Living for Elders (CAPABLE).⁶⁻⁹ CAPABLE is a person-centered, delivered at home by clinicians (occupational therapist [OT] and registered nurse [RN]), 20-week intervention supported by assistive devices and home modification to improve function and factors that impact function (i.e., balance, pain, depression).

The **goal** of this Stage Ib project is to examine implementation of CAPABLE in Home and Community Based Service waiver program sites (N=18) in MI. The waiver supports 15,000 low-income, nursing home eligible, disabled and older adults in the community, providing 19 services (i.e., personal care, meals, etc.) and case management through home visits by 575 clinicians (RNs and social workers [SW]). This research is premised on prior work that translated¹⁰⁻¹² CAPABLE at one site (Hartford/CMS; 2014); and pilot tested implementation strategies (MiCAP: training, facilitation, coalition building, audit and feedback) at four sites (Hillman/CMS; 2015-17).

Building on our prior work, objectives for this project are:

1. To test primary site-level outcomes of *adoption* and *sustainability* of CAPABLE after deploying MiCAP implementation strategies; and
2. To examine secondary beneficiary-level outcomes (*ADL/IADLs, pain, depression, falls, ED/hospital use*) after deploying MiCAP implementation strategies.

Work at 18 program sites will include readiness assessment, training, coalition building, audit, feedback, and facilitation. Internal facilitators (IFs) and external facilitators (EFs), who were prior work adopters of CAPABLE, will facilitate.

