1.14 DATA ANALYSIS

Preliminary analysis

The distributions of outcomes, mediators, and potential covariates will be assessed, outliers will be investigated by inspecting the residuals, and models described below will be fit with and without outliers to examine their influence on the results. Analyses will be implemented in SAS 9.4 as follows:

Aim A1 To test the effects of MiCAP with IF alone versus MiCAP with IF+EF with respect to the site-level outcomes of adoption and sustainability (**primary**) and beneficiary-level outcomes of ADL/IADLs, pain, depression, falls, emergency department (ED) visits and hospitalizations (**secondary**) over the next 12 months. Primary outcomes will be analyzed using a linear mixed effects model with repeated measures: 11 monthly measures of the SIC, 11 monthly summary records of clinician's actions based on EHR documentation, and monthly for 9 months measures from IF tools (statistical model #1). Covariates will include trial arm, variables used in randomization (site's size and CQAR score), and time entered as a class variable to model potentially non-linear patterns. In addition, we will use general liner model to analyze clinicians' fidelity training data. Log-rank test and Cox proportional hazard modeling will be employed to analyze time spent in each stage (treated as censored if a site does not complete a given implementation stage). The test of significance of the coefficient of the trial arm variable will yield the formal test of hypothesis associated with this aim for the main (time-averaged) effect of IF+EF v. IF alone. The analysis of secondary beneficiary-level outcomes will employ use generalized linear model with appropriately distributed errors and the random effect of site added to account for nesting of individuals within sites. For counts of falls and health service use, Poisson error distribution will be specified. Alternatively, as a zero-inflated Poisson or negative Binomial model based on the distribution of the counts will be fit. The explanatory variables including trial arm will be evaluated as predictors of zero inflation (whether or not the count is zero), and as predictors of the magnitude of the count when it is not zero. Pre-intervention MDS assessment will be used to obtain baseline version of each outcome, which will be included as a covariate to explain the variation in post-intervention outcomes.

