1.15 SAMPLE SIZE AND POWER CONSIDERATION

Aim 1: The sample size considerations for this study are based on the number of available sites given the project scope and timeline: N=18 sites will participate. With N=9 randomized to each condition, correlation of 0.7 between pairs of 11 repeated measures, the detectable adjusted effect size for the site-level outcomes is approximately 1.2, expressed as Cohen's d, difference between trial arm means in the standard deviation units. If the observed differences are smaller than 1.2 of the standard deviation, statistical significance will not be reached, then the estimate of the effect size will be obtained and used to formally power a subsequent R01-size study that will be proposed based on the results obtained in this R15 project. For the beneficiary-level outcomes, we assumed an average N=750 beneficiaries analyzed per site and conservative intraclass correlation coefficient of 0.01 for planning purposes to obtain the design effect factor DEFF=8.49. In the comparison of the trial arms for the beneficiary-level outcomes, the sample size adjusted for the design is 795 per trial arm, and it allows to detect the effect size as small as 0.14. Larger effects were seen in the preliminary studies for the beneficiary-level data, and 1/3 of the standard deviation or larger is often used as a threshold for clinical significance.⁸⁸⁻⁸⁹ Since even small effects could be detected as statistically significant, the study is well powered to detect any meaningful differences between IF and IF+EF in beneficiary outcomes. The tests of mediation effects in Aim 2 will have an even greater power because of further reduction in error variance due to controlling for the mediator. Aim 3 benchmarks the outcomes against the pre-intervention period and has no associated hypotheses. Thus, power considerations are not applicable. Similarly, exploratory aims 4-6 have no associated hypotheses; thus, the results will be used for generation of hypotheses for the future R01-scope trial.

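### If a zero-inflated model is used for falls, ED visits or hospitalisations, the plan reads its two parts as hurdle parts and names no overall arm test

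*Combined protocol and SAP*

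**What the plan says.** All of this is in section 1.14, Aim A1, unless stated otherwise.

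- First-named model: "For counts of falls and health service use, Poisson error distribution will be specified". It sits within a generalized linear model with "the random effect of site added to account for nesting of individuals within sites".
- Alternative: "Alternatively, as a zero-inflated Poisson or negative Binomial model based on the distribution of the counts will be fit". No criterion is given beyond the distribution itself. The phrase can mean a plain or a zero-inflated negative binomial.
- Reading of the alternative: "The explanatory variables including trial arm will be evaluated as predictors of zero inflation", with the two parts glossed as "zero inflation (whether or not the count is zero), and as predictors of the magnitude of the count when it is not zero". Arm therefore enters both parts.
- Formal test: "The test of significance of the coefficient of the trial arm variable will yield the formal test of hypothesis associated with this aim". The coefficient is singular, and the sentence goes on to describe a time-averaged effect, which fits the repeated-measures primary model best.

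The count outcomes are secondary; section 1.2 gives that objective as "To examine secondary beneficiary-level outcomes". The plan does not mention a hurdle model, a joint test of two arm coefficients, or an overall ratio derived from a two-part model.

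**The concern.** A zero-inflated model mixes two sources of zeros. The inflation part gives the probability of belonging to a group that can only produce zeros. The count part is an ordinary Poisson or negative binomial, which yields zeros of its own. Whether a person has any event depends on both parts, and so the inflation coefficient does not answer that question. Nor is the count coefficient the effect on the number of events among people who have at least one. A hurdle model does separate zero from non-zero and then models the non-zero counts; its parts match the plan's description.

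If the zero-inflated option is fitted and read as described, an arm difference in the chance of any fall, ED visit or hospitalisation could be reported as absent, and the difference among people with events could be overstated. Aim A1 asks whether IF+EF differs from IF alone on each outcome. Under this option that answer is spread over two coefficients, with nothing to say which one decides or how they combine. Aim A5 reuses the Aim 1 models with an arm-by-moderator term, so the same split would carry over to the moderator analysis.

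**Working it through.** **The plan's nearest figure.** Section 1.15 gives no figure for the count models. Its general power statement for beneficiary outcomes does reproduce:

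- Design effect = 1 + (750 − 1) × 0.01 = 8.49.
- The section says "With N=9 randomized to each condition", so effective n per arm = 9 × 750 / 8.49 = 795.
- Detectable d = (1.96 + 0.84) × √(2/795) = 0.14, assuming two-sided 5% and 80% power, neither of which is stated there.

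That calculation is for one arm comparison per outcome.

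**Formulas.** Let π be the structural-zero probability and λ the mean of the Poisson part.

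- Zero count: P(0) = π + (1 − π)e^(−λ)
- Mean among non-zero counts: λ / (1 − e^(−λ))
- Overall mean: (1 − π)λ

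**Inputs.** The documents give no event rates or zero fractions, so every π and λ below is an assumption.

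**Arm acts on λ only (π = 0.4 in both arms, λ 20% lower in one).** The inflation odds ratio is 1.00, and the count ratio and the overall mean ratio are both 0.80, in every row.

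| λ | P(0) | True zero-count OR | Mean among non-zero counts | True ratio |
|---|---|---|---|---|
| 0.3 v 0.24 | 0.844 v 0.872 | 1.25 | 1.157 v 1.125 | 0.97 |
| 1.0 v 0.8 | 0.621 v 0.670 | 1.24 | 1.582 v 1.453 | 0.92 |
| 2.0 v 1.6 | 0.481 v 0.521 | 1.17 | 2.313 v 2.005 | 0.87 |

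Middle row in full:

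- P(0) = 0.4 + 0.6e^(−1) = 0.621 and 0.4 + 0.6e^(−0.8) = 0.670.
- OR = (0.670/0.330) / (0.621/0.379) = 1.24.
- Ratio among non-zero counts = 1.453 / 1.582 = 0.92.

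Read as the plan describes, this is no effect on having any event and a 20% reduction among those with events. The truth is a zero-count odds ratio of 1.24 and a reduction of 8%. With λ 1.0 v 0.8 and π = 0.2 or 0.6, the zero-count odds ratio is 1.30 or 1.20.

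**Arm acts on π only (0.4 v 0.5, λ = 1).**

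- Inflation OR = (0.5/0.5) / (0.4/0.6) = 1.50.
- P(0) is 0.621 v 0.684, so the true zero-count OR is 1.32.
- The count ratio is 1.00, but the overall mean ratio is 0.5 / 0.6 = 0.83.

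**Opposing effects (π 0.4 v 0.5, λ 1.0 v 1.2).**

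- Inflation OR = 1.50 and count ratio = 1.20, both non-null.
- Overall means are 0.6 × 1.0 = 0.60 and 0.5 × 1.2 = 0.60, a ratio of 1.00.

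Neither coefficient alone, nor the pair read as described, shows that the arms have equal mean counts.

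**The case against.** The strongest reply is that this is a loose gloss on a fallback for secondary outcomes. Poisson comes first, and it and a plain negative binomial each have a single arm coefficient, which is a log rate ratio. The formal-test sentence can be read to cover that coefficient despite its time-averaged wording. The fitted zero-inflated model would itself be sound. When arm acts only on λ, its count ratio (0.80 above) equals the overall mean ratio, so the effect is reported and only its label is wrong.

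Most of this stands, and it limits the point. A reader might infer that arm effects on these outcomes will be misreported, or that the plan has no single arm test for counts. The documents do not support either, because both depend on the zero-inflated option being chosen. A reader might also count six arm tests in place of three. At an assumed 5% each and treated as independent, that would raise the chance of at least one false positive from 1 − 0.95³ = 14.3% to 1 − 0.95⁶ = 26.5%. It requires all three counts to go to the zero-inflated model, which nothing in the plan says, and two coefficients from one likelihood need not be independent. Finally, choosing a model from the count distribution does not imply looking at counts by arm. Section 1.14 does not say so, and section 1.16 restricts knowledge of assignment to the PI and PM.

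The reply does not cover the remaining cases. When arm acts on π, or on both parts, the count coefficient is not the overall ratio. The zero-inflated option is also the only one for which the plan says how arm will be interpreted, and that interpretation is wrong for the model named.

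**Conclusion.** The point holds conditionally. If a zero-inflated model is used for falls, ED visits or hospitalisations, the stated reading belongs to a hurdle model, arm effects could be misdescribed, and no joint or overall arm test is specified.

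Under the assumed 40% structural zeros and 20% lower Poisson mean, an inflation odds ratio of 1.00 would stand for a true zero-count odds ratio of about 1.17 to 1.25. A count ratio of 0.80 would stand for a true ratio of about 0.87 to 0.97 among non-zero counts. These figures show direction and plausible size; the size in this trial cannot be computed from the documents. The Poisson and plain negative binomial options are not affected, and neither is the site-level primary analysis. The matter is worth correcting because it governs what may be concluded for three secondary outcomes.

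**What to change.** In section 1.14, Aim A1:

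1. State that the single formal arm test for each count outcome is the arm ratio of overall mean counts, whichever count model is fitted. For Poisson or plain negative binomial this is the exponentiated arm coefficient. For a zero-inflated model, derive it as a marginal contrast from (1 − π)λ in each arm, averaged over the observed covariates, with a confidence interval that respects the clustering by site.
2. Either delete the two parenthetical readings or, if those two quantities are wanted, replace the zero-inflated model with a hurdle model.
3. State that the error distribution will be chosen on counts pooled over arms, and by what criterion.

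Making negative binomial the only model would also settle the matter, but that is a preference and is not needed.

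The cost is a few sentences of wording and a little extra programming for the marginal ratio and its interval. No data collection changes.

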Aim A2 Mechanism-of-action To determine whether the effects of EF+IF versus IF on primary outcomes are mediated by clinician attitude or self-efficacy at 9 months. In addition to statistical model #1, statistical model #2 will be fit at the clinician level with site as a random effect to account for nesting of clinicians within sites. To test for mediation, trial arm will be treated as the independent variable; each of the potential mediators (one at a time) will be tested for their effect on the outcome variable. We will use a bias corrected bootstrapping analytic strategy⁸⁶⁻⁸⁷ based on 5000 bootstrap samples to estimate confidence intervals around the indirect effect of the trial arm on the outcome variable, through the mediator. To establish mediation, the 95% confidence interval around the indirect must not include 0.

Aim A3 To benchmark the effects of IF and EF+IF on beneficiary outcomes following implementation as compared to pre-intervention. The analysis of this aim will use 2 repeated measures of beneficiary outcomes: at the start of this study (pre-intervention) and in the following 12 months. Time by trial arm interaction will be included. The least square (LS) means according to the interaction term will be output from this model, and differences from pre-to-post CAPABLE will be evaluated for each arm to gauge the magnitude and practical meaning of improvements.

Exploratory Aim A4 To compare the primary and secondary outcomes within 12 months, potential mediators at 9 months, and baseline leadership and readiness for sites with SIC of $>50\%$ versus sites with $SIC \leq 50\%$ at 6 months in each arm. General or generalized linear models (as appropriate based on outcome or potential mediator distribution) will include the binary indicator of whether SIC at 6 months is $>50\%$ or $<50\%$ in interaction with the trial arm variable. Differences between LS means according to SIC level will be tested within each arm. Because these analyses are exploratory, in addition to formal tests of significance, the effect sizes will be estimated.

Exploratory Aim A5 To explore whether baseline site leadership and readiness moderate the impact of EF+IF compared to IF on primary and secondary outcomes within 12 months in order to determine which sites may

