require facilitation that is more intensive. To address this aim, statistical models described under analysis for Aim 1 will be modified to include trial arm by potential moderator interaction. The effect sizes that correspond to the interaction term will be estimated.

Exploratory Aim A6 To evaluate clinician satisfaction at 1 month, and the cost of implementation and policy impact for IF and IF+EF at 12 months. We will use descriptive statistics to summarize clinician satisfaction with training and the cost of implementation. We will use qualitative thematic analysis to analyze all qualitative data on survey tools. We will report on the policy impact as evidenced in the State Contract for the Medicaid Waiver program.

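### Exploratory Aim A4 states no site effect for its tests of beneficiary outcomes and clinician mediators between SIC groups of sites; fitted as written, a 5% beneficiary test would reject about 50% of the time at the plan's planning values

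*Combined protocol and SAP*

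**What the plan says.** Section 1.14 describes A4 as intended "To compare the primary and secondary outcomes within 12 months, potential mediators at 9 months, and baseline leadership and readiness for sites with SIC of" above 50% at 6 months against the remaining sites, in each arm. Three features of the A4 text matter.

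- **Model.** "General or generalized linear models (as appropriate based on outcome or potential mediator distribution) will include the binary indicator" of SIC group, in interaction with trial arm. No site term is named, and there is no reference to a model defined elsewhere.
- **Test.** "Differences between LS means according to SIC level will be tested within each arm".
- **Status.** "Because these analyses are exploratory, in addition to formal tests of significance, the effect sizes will be estimated". Section 1.15 adds that aims 4 to 6 carry no hypotheses and serve to generate them for a later, larger trial.

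The neighbouring aims are more explicit. For beneficiary outcomes, A1 also starts from a generalized linear model, but with "the random effect of site added to account for nesting of individuals within sites". A2 fits its clinician-level model #2 with a random site effect. A5 says that "statistical models described under analysis for Aim 1 will be modified to include trial arm by potential moderator interaction", so it inherits the A1 structure.

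Section 1.15 recognises the clustering when it sizes the beneficiary comparison. It takes an average of 750 beneficiaries per site and a "conservative intraclass correlation coefficient of 0.01 for planning purposes to obtain the design effect factor DEFF=8.49".

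**The concern.** SIC group is a property of the site, so each within-arm contrast sets some of 9 sites against the others. The information about such a contrast comes mainly from the number of sites. An independent-error model takes its standard error from the number of people instead, and so counts ordinary site-to-site variation as if it were evidence about SIC.

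Two families of A4 outcomes are individual-level data exposed to this: the beneficiary outcomes from the MDS, and clinician attitude and self-efficacy at 9 months. At stake are the p-values that A4 promises, which would help choose hypotheses for the next trial. Differences between high-SIC and low-SIC sites could be carried forward when they are only background variation between sites.

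**Working it through.** **Inputs.**

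- From section 1.15: 9 sites per arm, m = 750 beneficiaries per site, ICC = 0.01, design effect 8.49, 795 effective beneficiaries per arm, detectable effect 0.14.
- From section 1.5: 575 clinicians and 18 sites.
- Assumed: two-sided alpha of 0.05, because A4 and section 1.15 state none. With 80% power this level reproduces the plan's detectable effect (step 1).
- Assumed: clinician ICC from 0.01 to 0.10, because the documents give none.

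**Step 1. Reproduce the plan's figures.**

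- DEFF = 1 + (m − 1) × ICC = 1 + 749 × 0.01 = 8.49, as stated.
- Effective n per arm = 9 × 750 / 8.49 = 795, as stated.
- Detectable effect = (1.960 + 0.842) × √(2/795) = 0.1405, against 0.14 stated.

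**Step 2. Effect of leaving the site out of A4.** With equal site sizes, the true variance of each SIC-group mean is DEFF times the variance that an independent-error model assigns, whatever the split of sites. The standard error is therefore too small by √DEFF, and the real rejection rate of a nominal 5% test under no difference is

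2 × (1 − Φ(1.96 / √DEFF)).

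At DEFF 8.49, √DEFF = 2.91 and 1.96 / 2.91 = 0.673, which gives **50.1%**.

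| Outcome | Per site | ICC | DEFF | False-positive rate |
|---|---|---|---|---|
| Beneficiary | 750 | 0.001 | 1.75 | 13.8% |
| Beneficiary | 750 | 0.005 | 4.75 | 36.8% |
| Beneficiary | 750 | 0.01 (plan) | 8.49 | 50.1% |
| Beneficiary | 750 | 0.02 | 15.98 | 62.4% |
| Beneficiary | 400 | 0.01 | 4.99 | 38.0% |
| Beneficiary | 100 | 0.01 | 1.99 | 16.5% |
| Clinician | 575/18 = 31.9 | 0.01 | 1.31 | 8.7% |
| Clinician | 31.9 | 0.05 | 2.55 | 21.9% |
| Clinician | 31.9 | 0.10 | 4.09 | 33.3% |

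The figure of 32 clinicians per site is a ceiling. It counts everyone employed, whereas section 1.7 includes only clinicians trained in CAPABLE and section 1.17 only those who consent.

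**Step 3. Check by simulation.** The four-cell model (arm by SIC group) was simulated with no true difference: 18 sites, m = 750, ICC 0.01, 40,000 runs per setting. For splits of 4/5, 3/6, 2/7 and 1/8 sites in the tested arm, the independent-error test rejected in 50.0% to 50.3% of runs. With assumed uneven site sizes (200 to 1,550, mean 750) it rejected in 54.5%.

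**Step 4. The same contrast with the site as the unit.** Analysing site means on 18 − 4 = 14 degrees of freedom rejected in 4.8% to 5.1% of the same settings, and in 4.9% with uneven sites. If site size and CQAR score are carried over from A1 as linear covariates, 18 − 4 − 2 = 12 degrees of freedom remain.

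**The case against.** The strongest reply is that silence is not a decision. A4 says what its models will include and does not claim to list every term; it also omits the baseline outcome, site size and CQAR. In A1 the generalized linear model is the base to which a site effect is added, so the label does not rule one out. A3, and A1's model for clinician training data, do not mention site either. All this is fair. A reader might infer that the plan chose to ignore clustering in A4, and the documents do not support that. If the analyst carries over the A1 structure, the inflation does not arise. What stands is that A4 names its own model class and formal tests, that A5 in the next paragraph expressly imports the A1 models, and that an analyst following A4 literally would fit independent errors.

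Some wider readings are also tempting and should not be drawn.

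- **Leadership and readiness as clinician rows.** Clinicians answer these scales, but section 1.12 lists both as site-level data and its measures table gives sites as the unit measured. With one score per site, a general linear model needs no site effect.
- **The monthly primary series.** Eleven measures correlated at 0.7 give a factor of 1 + 10 × 0.7 = 8 and a rate of 48.8%, but only if months enter A4 as independent rows. A4 speaks of outcomes within 12 months, and one summary per site fits that wording.
- **SIC as an A4 outcome.** The groups are formed from month-6 SIC, so a null of no SIC difference is untenable from the start and a false-positive rate has no meaning there.
- **Intervals of the wrong width.** A4 promises tests and effect sizes, not confidence intervals. The damage is to standard errors and p-values.

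Exploratory status limits the consequence, since no primary or secondary conclusion depends on A4. It does not make a test with the wrong error rate useful for choosing hypotheses.

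**Conclusion.** The point holds for beneficiary outcomes and for the two clinician mediators at 9 months. As written, A4 tests individual-level data on a site-level factor with no stated allowance for site, and a literal fit gives wrong p-values.

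The 50% for a beneficiary outcome is conditional on an average of 750 per site, an ICC of 0.01 (which the plan itself calls conservative), a two-sided 5% level that is inferred, and a literal reading of the model sentence. At 750 per site the rate runs from 14% to 62% for ICCs from 0.001 to 0.02. The clinician range of 9% to 33% rests on an assumed ICC and on a cluster size that is an upper limit. The point does not extend to leadership and readiness scored once per site, or to site outcomes summarised once per site. It has no bearing on the primary analysis.

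**What to change.** Replace the A4 model sentence with text to this effect:

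> *Beneficiary outcomes will be analysed with the Aim A1 generalized linear mixed model, and clinician attitude and self-efficacy with model #2, each keeping its random site effect and extended with the month-6 SIC indicator and its interaction with arm. SIC contrasts will be tested with between-site degrees of freedom (about 14 without site-level covariates, about 12 with site size and CQAR score). Leadership and readiness will be analysed as one score per site. Any site-level outcome entered as monthly rows will keep the repeated-measures structure of model #1. SIC itself will be described, not formally tested, between groups defined by SIC.*

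An analysis of site means is an acceptable alternative for the beneficiary and clinician outcomes. If leadership or readiness is analysed from clinician rows, it too needs a random site effect. The significance level for A4 should be stated in the same place.

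The cost is a short revision of section 1.14 and a RANDOM statement (or REPEATED for monthly rows) in the SAS code, with no new data. The downside is that standard errors widen, by a factor of about 2.9 for beneficiary outcomes at the planning values, and fewer exploratory differences will reach significance.
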